1 STUDY SYNOPSIS

1.1 Overview

The objective of this study is to gain preliminary information regarding the clinical effects of Vascular and the possible role of the glycocalyx as a physiological target for Vasculera activity. It is anticipated that the results of the results of this study will inform the development of a randomized, double-bline, place controlled trial.

Study design: This is an open-label case study. This study will consist of a single 3-month treatment period.

In order to evaluate the efficacy, exploratory, and safety endpoints, study assessments will be conducted at screening/baseline (visit 1), visit 2 (month 1), visit 3 (month 2) and end-of-study (visit 4, month 3).

Study population: The planned sample size for this study is 30 subjects with lipedema present for at least 1 year who have not taken any diosmin containing medications within the 1 year prior to screening and meet all other inclusion and exclusion criteria.

Investigational Products: The investigational product is Vasculera® 1260 mg/day (one 630 mg tablet administered twice a day).

Efficacy Outcomes: The efficacy outcomes are the changes in the following clinical assessments from baseline to month 3:

Weight

Leg circumference 2 and 12 inches above lateral malleoli of both legs

Body mass index (BMI)

Short Western Ontario and McMaster Universities Osteoarthritis Index (WOMAC) total score

Subject assessments, on a 0-10 scale (10=worst), for:

Leg discomfort

Feeling of leg swelling/tightness

Leg tenderness

Leg bruising

Leg skin redness

Fatique

Ability to perform activities of daily living (ADL)

Overall sense of well-being

Investigator assessment of response to therapy by Likert scale (0-5)

Sample Size: The planned sample size for this study is 30 subjects. Because this is an exploratory study, no formal sample size calculations were completed.

1.2 Efficacy Outcomes

Efficacy outcomes include the following clinical assessments:

Change in weight from basline to month 3;

Change in leg circumference, measured 2 and 12 inches above lateral malleoli of both legs, from baseline to month 3;

Change in body mass index (BMI) from baseline to month 3;

Change in the short WOMAC total score from baseline to month 3;

Changes in the following subject assessments from baseline to month 3:

Leg discomfort

Feeling of leg swelling/tightness

Leg tenderness

Leg bruising

Leg skin redness

Fatigue

Ability to perform activities of daily living (ADL)

Overall sense of well-being;

Investigator assessment of response to therapy at month 3.

1.3 Exploratory Outcomes

Exploratory outcomes include changes in plasma glycocalyx markers from baseline to month 3.

1.4 Safety Outcomes

Safety outcomes will include adverse events (AEs) reported at month 1, month 2, and month 3.

2 Statistical Analysis

2.1 Hypothesis Tests

All efficacy, secondary, and safety outcomes will be tested using a two-sided alpha of 0.05 with recognition of the increased risk of making a type I error due to testing of multiple outcomes.

Statistical analyses will be conducted using IBM SPSS Statistics for Windows, version 24 or higher (IBM Corp., Armonk, N.Y., USA).

2.2 Analytical Populations

The populations for analysis will include the following:

The **Safety Population** will consist of all subjects who received any amount of study product, and on whom any post-enrollment safety information is available.

The modified **Intent-to-Treat (ITT) Population** consists of subjects in the safety population who provided any post-enrollment information on the efficacy outcomes.

The **Per Protocol (PP) Population** consists of all subjects who consumed 80% to 120% (inclusive) of study product doses, do not have any major protocol violations and complete all study visits and procedures connected with measurement of the efficacy outcomes.

All outcomes will be analyzed for the ITT and PP populations. The safety endpoints will be analyzed for the Safety population.

2.3 Demographic and Screening/Baseline Characteristics

Demographic and screening/baseline characteristics of the enrolled subjects will be presented (e.g., age, gender, race/ethnicity). Descriptive statistics [number of subjects, mean, standard error of the mean (SEM), median, minimum, maximum, and interquartile range] will be reported for continuous variables. Frequency and percent of total will be reported for categorical variables.

2.4 Continuous Outcomes

Descriptive statistics [number of subjects, mean, standard error of the mean (SEM), median, minimum, maximum, and interquartile range] will be presented for the following outcomes at screening/baseline, month 1, month 2, and month 3: weight, leg circumference, short WOMAC individual item scores, short WOMAC total score, leg discomfort, leg swelling/ tightness, leg tenderness, leg bruising, leg skin redness, fatigue, ability to perform ADL, and overall sense of well-being. Descriptive statistics for BMI and plasma glycocalyx markers will be presented at screening/baseline and month 3. Descriptive statistics for the change from baseline to each corresponding post-enrollment time point will also be presented for the above outcomes. Descriptive statistics will be presented for response to treatment at month 3.

The short WOMAC score will be calculated by summing the individual item scores (formula provided below). Each item will be scored as follows: None=0, Mild=1, Moderate=2, Severe=3, Extreme=4.

Short WOMAC score =
$$\sum_{i=1}^{8} (Score \ for \ item_i)$$

Leg discomfort, leg swelling/tightness, leg tenderness, leg bruising, and leg skin redness will be reported as a number ranging from 0 to 10 where 0= "none" and 10= "worst you have ever seen or felt". These outcomes will be treated as scale variables.

Fatigue, ability to engage in ADL, and overall sense of well-being will be reported as a number ranging from 0 to 10 where 0= "none" and 10= "worst you have ever felt". These outcomes will be treated as scale variables.

Response to treatment will be assessed using a Likert scale (0-5). Response to treatment will be treated as a scale variable.

Change from baseline will be calculated as:

Change from Baseline to $Visit_i = (Value \ at \ Visit_i) - (Value \ at \ baseline)$

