 - overall sense of well-being
- 6- Investigator assessment of response to therapy by 5-point Likert scale

Exploratory Measures

Plasma glycocalyx markers

Safety measurements

Adverse event recording

Study product dosing and rationale

Vasculera 630 mg BID

Vasculera is marketed for management of venous insufficiency at a dose of 630 mg (one tablet, 95% purity) daily. Most of the literature, almost all of which is from historical use in Europe uses doses of 500 mg (90% purity) BID. The literature suggests that 600 mg of 95% product is the equivalent of 500 mg of 90% product for treatment of the early stages of CVI but anecdotal evidence suggest that BID dosing of Vasculera performs better than QD dosing in more severe stages of CVI and other disorders.

Inclusion criteria

- 1- established diagnosis of lipedema (see Appendix III) for at least one (1) year
- 2- women, ages 20 to 70 years
- 3- score of at least 4 out of 10 on a rating scale of 0-10 (10=worst) for overall sense of well being
- 4- able to read and understand Informed Consent Document (ICD) and all questionnaires in English or with family/friend translator
- 5- not pregnant or lactating; women of child bearing potential must use an approved method of birth control (Appendix II).
- 6- be willing to stop compression therapy for one week prior to each visit

Exclusion criteria

- 1- other forms of leg enlargement, including lymphedema without coexisting lipedema
- 2- any primary systemic vasculopathy
- 3- history of exposure to Vasculera or other diosmin containing medication within one (1) year of the screening visit
- 4- concomitant use of warfarin, platelet inhibitors, factor Xa inhibitors or any medication intended to reduce blood coagulability
- 5- concomitant use of diclofenac, metronidazole or chlorzoxazone
- 6- uncontrolled hypertension (BP>170/110), unstable cardiac disease, active skin ulceration
- 7- any other disease or condition that, in the opinion of the investigator, might put the subject at risk by participation in this study OR confound evaluation of response to Vasculera
- 7- history of substance abuse within one (1) year of the screening visit or of current alcohol consumption more than one (1) unit daily. For purposes of this study, a unit of alcohol will be considered to be 12 oz of beer, 6 oz of wine or 1 ^ oz of hard spirits.

Number of subjects

It is estimated that 30 subjects will be sufficient to obtain a meaningful efficacy signal.

Length of study

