5.0 Study selection criteria

5.1 Inclusion criteria

- 1-established diagnosis of lipedema (see appendix III) for at least one (1) year
- 2-women, ages 20 to 70 years
- 3-score of at least 4 out of 10 on self-assessment on a 0-10 scale (10=worst) for overall sense of well being
- 4-able to read and understand all questionnaires in English or with family/friend translator
- 5-not pregnant or lactating; women of child bearing potential should use an approved method of birth control for the duration of the study

6-be willing to stop compression therapy for one week prior to each visit

5.2 exclusion criteria

- 1- other forms of leg enlargement, including lymphedema
- 2- any primary systemic vasculopathy
- 3- history of exposure to Vasculera or other diosmin containing medication within one (1) year of the screening visit
- 4- concomitant use of warfarin, platelet inhibitors, factor Xa inhibitors or any medication intended to reduce blood coagulability
- 5- concomitant use of diclofenac, metronidazole or chlorzoxazone
- 6- uncontrolled hypertension (BP>170/110), unstable cardiac disease, active skin ulceration
- 7- any other disease or condition that, in the opinion of the investigator, might put the subject at risk by participation in this study OR confound evaluation of response to Vasculera
- 8- history of substance abuse within one (1) year of the screening visit or of current alcohol consumption more than one (1) unit daily. For purposes of this study, a unit of alcohol will be considered to be 12 oz of beer, 6 oz of wine or 1 'A oz of hard spirits.

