2.5 Analysis of Continuous Outcomes

For weight, leg circumference, short WOMAC total score, leg discomfort, leg swelling/tightness, leg tenderness, leg bruising, leg skin redness, fatigue, ability to perform ADL, and overall sense of well-being, change from baseline to each post-enrollment time point will be assessed using a repeated measures ANCOVA model with baseline value included as a covariate. Least square means (LSMs) will be calculated for the change from baseline to each time point. In the case of nonnormality, a rank transformation will be applied and medians and interquartile limits will be reported. The change from baseline to each post-enrollment time point will be tested independently, however the primary time point for effacicy analysis will be change from baseline to month 3.

For BMI and plasma glycocalyx markers, change from baseline to month 3 will be assessed using a paired t-test or the Wilcoxon signed rank test, depending on the distribution of the data.

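### The 0–10 items for ability in daily activities and for well-being have a lower anchor that contradicts their scoring direction

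*SAP*

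**What the plan says.** SAP 2.4 groups three items: "Fatigue, ability to engage in ADL, and overall sense of well-being will be reported as a number ranging from 0 to 10", and gives them one pair of anchors: "where 0= 'none' and 10= 'worst you have ever felt". It puts the anchors in quotation marks, so they may be the words on the form.

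The intended direction is consistent throughout. SAP 1.1 introduces all eight self-ratings as "Subject assessments, on a 0-10 scale (10=worst), for". Inclusion criterion 3 in protocol 5.1 requires a "score of at least 4 out of 10 on self-assessment on a 0-10 scale (10=worst) for overall sense of well being", and the synopsis version agrees: "score of at least 4 out of 10 on a rating scale of 0-10 (10=worst) for overall sense of well being".

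Both items are efficacy outcomes, listed in SAP 1.2 under "Changes in the following subject assessments from baseline to month 3". Under SAP 2.5 their change "will be assessed using a repeated measures ANCOVA model with baseline value included as a covariate", and SAP 2.1 has outcomes "tested using a two-sided alpha of 0.05". Change is defined in SAP 2.4 as the visit value minus the baseline value. Protocol section 16 says that only variables clearly affected by treatment go forward to the formal trial.

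Neither document describes an instruction to subjects about direction, a check of direction, or a recoding rule. The questionnaire is not included.

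**The concern.** A lower anchor of none works when the item names a complaint. When the item names something desirable, none is the bad end. For ability in daily activities and for well-being, 0 therefore literally describes the worst state while being scored as the best, and 10 is also labelled as bad. A subject who feels well has no anchor that describes her.

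The 10 = worst statements tell the analyst how to code the number. They do not settle how a subject reads the 0. Inclusion criterion 4 allows questionnaires to be completed through a family or friend translator, so literal wording matters more than usual.

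Two things are at stake: whether change on two of the eight self-ratings is recorded with the right sign, and whether the well-being threshold classifies subjects correctly at entry. Because the study exists partly to select outcomes for a later trial, a misread item could be dropped or kept for the wrong reason.

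**Working it through.** **Inputs.** The anchors and the definition of change are from SAP 2.4, the direction from SAP 1.1, and the threshold of at least 4 from inclusion criterion 3. SAP 1.1 plans 30 subjects without a formal calculation. The documents give no effect size, SD, power or reversal share, so there is no stated figure to reproduce.

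**Step 1: anchors against direction.**

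| Item | Literal meaning of 0 = none | Scored as | Consistent? |
|---|---|---|---|
| Fatigue | no fatigue (good) | best | yes |
| Ability in daily activities | no ability (worst) | best | no |
| Overall well-being | no well-being (worst) | best | no |

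**Step 2: effect on recorded change.** Let b and m be the true baseline and month-3 scores (10 = worst). A reversed answer is recorded as 10 − true.

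- Reversed at both visits: (10 − m) − (10 − b) = −(m − b). A true 7 to 5 (−2) is recorded as 3 to 5 (+2).
- Reversed at baseline only: m − (10 − b). A true 8 to 6 (−2) becomes 6 − 2 = +4.
- Reversed at month 3 only: (10 − m) − b. The same true change becomes 4 − 8 = −4.

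Consistent reversal flips the sign. Switching can either hide or exaggerate improvement.

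**Step 3: effect on entry.** A true score T qualifies if T ≥ 4. When reversed, the recorded score qualifies if 10 − T ≥ 4, that is, T ≤ 6.

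| True score | Recorded if reversed | Should enter | Would enter |
|---|---|---|---|
| 0–3 | 10–7 | no | yes |
| 4–6 | 6–4 | yes | yes |
| 7–10 | 3–0 | yes | no |

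**Step 4: can a group-level size be given?** If a share f of those analysed reverse at every visit and their true change δ matches everyone else's, the mean recorded change is (1 − f)δ − fδ = (1 − 2f)δ; for example 0.8δ at f = 10%. The share f is unknown, and for well-being Step 3 undermines the rest: a woman who reverses at screening enrols only if T ≤ 6, so enrolled reversers are fewer and have less room to improve.

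Illustration, with every input assumed: T normal with SD 2, rounded to whole numbers; 10% reverse at screening. The share of reversers among those enrolled is 0.1·P(T ≤ 6) / [0.1·P(T ≤ 6) + 0.9·P(T ≥ 4)].

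- Mean 5: 0.0773 / (0.0773 + 0.6960) = 10%
- Mean 6: 0.0599 / (0.0599 + 0.8050) = 7%
- Mean 7: 0.0401 / (0.0401 + 0.8639) = 4%

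The share wrongly admitted (T ≤ 3), over the same denominators, is about 3%, 1% and 0.4%. Changing one assumed mean moves the share of reversers from 10% to 4%, before f itself is varied. No single figure can be defended.

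**The case against.** The strongest reply is that the harm depends on a form nobody can see here. The direction is stated the same way everywhere, and the form may print it. The two items come last in the list, after six on which a higher score is plainly worse; if the form keeps that order, it cues the intended reading. The documents contain no evidence that anyone answers in reverse. The study is exploratory, and weight, circumference, BMI, WOMAC, the investigator rating and the markers are untouched.

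This stands as a limit on consequence and importance. It does not remove the conflict between item name and lower anchor, which is in the SAP's own text.

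Three stronger readings are tempting, and the documents do not support them:

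- *That the trial loses a calculable amount of power.* The reversal share, effect and SD would all have to be invented. A paired t-test, named in protocol section 16, is not the SAP's repeated measures ANCOVA for these items. Entry itself screens out some reversers. No planned power exists to be lost.
- *That the outcomes are always pulled toward zero.* That describes consistent reversal under the Step 4 assumptions; switching between visits can push either way.
- *That well-being is the only symptom-based entry criterion, so the study population is compromised.* Criterion 1 requires an established lipedema diagnosis under Appendix III, whose features include pain, tenderness and easy bruising. Well-being is only the sole numeric self-rating threshold. A woman wrongly admitted on it would still need that diagnosis.

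**Conclusion.** The point holds as a defect in the wording of two items. SAP 2.4 applies an anchor pair written for complaints to two positively worded items, so the 0 anchor contradicts the direction of scoring and no anchor names a good state. For any individual who answers in reverse, the sign error and the entry misclassification follow by arithmetic.

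How many subjects do so is unknown. The conclusion therefore covers what can happen to a subject's data, not how far a mean or a test result is moved. The shares in Step 4 are illustrations only. If the form already carries clear good-end wording, the remaining task is to quote it in the SAP. The defect is worth correcting because the study's purpose is to choose outcomes and the correction is small; it does not threaten the other endpoints.

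**What to change.** Give the two items their own anchors, each with an explicit good end. For example: 'difficulty performing ADL', 0 = no difficulty, 10 = worst difficulty; and 'overall well-being', 0 = best possible, 10 = worst possible. Use identical wording in the CRF, protocol 4.0 and 4.2, SAP 2.4 and inclusion criterion 3, and wherever the synopsis, visit lists and schedule repeat the item names. Leave the entry threshold unchanged. Fatigue can keep its present anchors.

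If data have already been collected, do not recode individual answers. Before lock, pre-specify a sensitivity analysis with a fixed numerical rule for flagging subjects whose direction on these two items conflicts with their leg-symptom items, and report results with and without them. The analysis of all subjects should stay the main one: well-being can genuinely move apart from leg symptoms, and in an open-label study a rule chosen after seeing results would invite outcome-driven exclusion.

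The cost is rewording two items and the matching text, plus a small protocol amendment handled with the IRB under protocol 12.2. No extra visits or subjects are needed.

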2.5 Analysis of Continuous Outcomes

For weight, leg circumference, short WOMAC total score, leg discomfort, leg swelling/tightness, leg tenderness, leg bruising, leg skin redness, fatigue, ability to perform ADL, and overall sense of well-being, change from baseline to each post-enrollment time point will be assessed using a repeated measures ANCOVA model with baseline value included as a covariate. Least square means (LSMs) will be calculated for the change from baseline to each time point. In the case of nonnormality, a rank transformation will be applied and medians and interquartile limits will be reported. The change from baseline to each post-enrollment time point will be tested independently, however the primary time point for effacicy analysis will be change from baseline to month 3.

For BMI and plasma glycocalyx markers, change from baseline to month 3 will be assessed using a paired t-test or the Wilcoxon signed rank test, depending on the distribution of the data.

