3.1 Assessment of Model Fit

Assumptions of normality of residuals will be investigated for each continuous outcome. Normality will be assessed by examining blox plots, Q-Q plots, measures of skewness and kurtosis, and the results of Shapiro-Wilk tests. In the case of nonnormality, a rank transformation will be applied and medians and interquartile limits will be reported.

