3.2 Missing Data

Missing outcome data will estimated using multiple imputation.

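### The SAP's rank-transformation fallback is not defined for a one-arm analysis of change: ordinary ranks lose the position of zero, and two natural readings give a p-value unrelated to the change

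*SAP*

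**What the plan says.** SAP 2.5 analyses 11 outcomes (weight, leg circumference, short WOMAC total and the eight 0-10 ratings) with a repeated measures ANCOVA of change, adjusted for baseline. If the four leg sites (two heights, two legs) are modelled separately, that is 11 − 1 + 4 = 14 variables. On estimation: "Least square means (LSMs) will be calculated for the change from baseline to each time point". On testing: "The change from baseline to each post-enrollment time point will be tested independently", with month 3 as the main time point. SAP 2.1 sets a two-sided alpha of 0.05. There is no control group; Protocol 3.0 gives every subject the same product.

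The fallback in SAP 2.5 is: "In the case of nonnormality, a rank transformation will be applied and medians and interquartile limits will be reported". SAP 3.1 repeats the sentence without further detail and describes the check behind it: "Normality will be assessed by examining blox plots, Q-Q plots, measures of skewness and kurtosis, and the results of Shapiro-Wilk tests". No threshold is given.

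BMI and the plasma markers are treated differently. For them, "change from baseline to month 3 will be assessed using a paired t-test or the Wilcoxon signed rank test", according to the distribution of the data. Two other provisions bear on the point. SAP 2.4 states: "Descriptive statistics for the change from baseline to each corresponding post-enrollment time point will also be presented for the above outcomes". SAP 3.2 states: "Missing outcome data will estimated using multiple imputation".

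**The concern.** In a trial with two arms, ranking the response still lets the model compare the arms. Here there is one arm, and the only reference is zero change. Adding the same constant to every subject's change leaves the ordinary ranks untouched, so those ranks cannot show whether the typical change is above, at or below zero. The SAP does not say whether raw values or changes are ranked, whether ranking is within or across visits, whether ranks carry a sign, or what value the least squares mean of the ranks is tested against.

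The p-value for an outcome sent to the fallback could therefore depend on how an analyst reads one sentence. Protocol section 16 intends the formal trial to carry forward only outcomes on which an effect is clear, so a false or missed signal bears directly on the study's stated use.

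**Working it through.** The documents give no effect size, SD or power calculation, so there is no figure of the plan's own to reproduce. Inputs from the documents: n = 30 (SAP 1.1), two-sided alpha 0.05 (SAP 2.1), change = visit value minus baseline (SAP 2.4), one arm (Protocol 3.0).

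**(a) Rank the changes and test their mean against zero.** Untied ranks 1 to n have mean (n+1)/2 and SD sqrt(n(n+1)/12).
- At n = 30: mean 15.5, SD sqrt(30 × 31/12) = 8.80.
- t = 15.5/(8.80/sqrt(30)) = 9.64 = sqrt(3 × 31), 29 df, p = 1.5e-10.
- This is the same whether all subjects improve, none change or all worsen.
- With one covariate in a single-visit ANCOVA, the residual sum of squares cannot exceed the total, so t ≥ 9.64 × sqrt(28/29) = 9.48 (28 df, p = 3.1e-10).
- Ties only raise t. For 20 zeros, five −1 and five +1, the mid-ranks are 15.5, 3 and 28. The SD is sqrt(10 × 12.5²/29) = 7.34, so t = 15.5/(7.34/sqrt(30)) = 11.57, p = 2.2e-12. The paired t-test and signed rank test on the same changes give p = 1.0.
- Against the mid-rank 15.5 instead of zero, p = 1 always.

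**(b) Rank values within each visit, then difference.** With the same 30 subjects at both visits the mean rank is 15.5 each time, ties or not. The mean difference is 15.5 − 15.5 = 0 and p = 1 for any data.

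**(c) Rank baseline and visit values jointly, then difference**, and **(d) signed ranks of the change.** Both keep the position of zero.

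Simulation check: n = 30, month-3 ANCOVA with the least squares mean at mean baseline, heavy-tailed errors, values rounded to a 0-10 scale, 1,500 replicates per row. True changes and SDs are assumptions. Rejection at two-sided 0.05:

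| True change | (a) | (b) | (c) in ANCOVA | (d) in ANCOVA | Wilcoxon signed rank | Untransformed ANCOVA |
|---|---|---|---|---|---|---|
| 0 | 100% | 0% | 7.5% | 6.8% | 5.2% | 6.8% |
| −1 | 100% | 0% | 90.2% | 91.4% | 87.5% | 89.3% |
| −3 | 100% | 0% | 100% | 100% | 100% | 100% |
| +1 | 100% | 0% | 88.1% | 90.3% | 85.8% | 85.5% |

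Ranking the changes pooled over the three visits and testing month 3 against zero does not rescue (a): it also rejected 100% of the time with no change.

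A second simulation used an assumed integer item with mean 4, SD 2.5, no change and correlation 0.3/0.6/0.8 between visits. Joint ranks in the ANCOVA rejected 10.8/7.9/6.0%, against 10.7/7.7/6.0% for the untransformed ANCOVA. The excess over 5% comes from testing the least squares mean with baseline treated as fixed, not from ranking.

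**The case against.** The strongest reply is that the SAP never tells the analyst to test a mean rank against zero, that two of the four readings work, and that the degenerate ones give themselves away. Without ties or covariate, reading (a) returns the same p-value for every outcome, and (b) returns exactly 1. SAP 2.4 puts original-scale changes beside them, and the fallback itself asks for medians and interquartile limits. A median change of 0 next to p near 1e-10 would hardly pass as a clear effect. The study is also exploratory, and SAP 2.1 acknowledges multiple testing. All of this stands and limits the harm. It does not supply the missing definition, and the choice would be made with the data in hand.

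A reader might infer three stronger things that the documents do not support.

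- *That dropout makes reading (b) reject spuriously in favour of improvement.* This needs all subjects ranked at baseline but only those observed at month 3. The modified ITT set does admit anyone "who provided any post-enrollment information on the efficacy outcomes", but the plain reading of SAP 3.2 is to impute missing outcomes, so the same subjects are ranked at both visits and (b) still never rejects. The per-protocol set requires complete visits.
- *That the fallback will probably be triggered.* The documents give no data on the distributions and no threshold. Under an assumed Shapiro-Wilk cut of 0.05, simulated trigger rates ran from 5-7% for a mid-scale item to 55-77% for one with 40% zeros at baseline. That range is set by the assumed floor. Overall well-being cannot have such a floor at baseline, because entry requires a score of at least 4 (Protocol 5.1). SAP 3.1 also weighs several diagnostics together, and the leg-symptom ratings come from the same subjects and are unlikely to be independent.
- *That joint ranking inflates the error rate.* It matches the untransformed model.

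**Conclusion.** The concern holds: the fallback is undefined for a one-arm change analysis, and two natural readings return a p-value that carries no information about change, rejecting always or never. That result is algebraic and needs no assumed effect size. The bound of 9.48 applies to a single-visit ANCOVA, and the simulations likewise use one visit, not the full repeated-measures model. The count of two in four depends on how the readings are listed.

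The reach is limited to the 11 ANCOVA outcomes, and only if non-normality is declared; how often that would happen is unknown. BMI, the glycocalyx markers, the investigator's response scale, the original-scale summaries and the protocol's paired t-test (Protocol section 16) are unaffected. The documents do not show that the trial would report false signals, only that the written rule permits p-values unrelated to the change. It should be settled before the outcome data are analysed.

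**What to change.** In SAP 2.5 and 3.1, replace the rank-transformation sentence with:

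> If residuals are non-normal, the change from baseline at each visit (month 3 primary) will be tested against zero with the Wilcoxon signed rank test, as for BMI and the glycocalyx markers, and the median change with interquartile limits and the Hodges-Lehmann estimate with 95% CI will be reported.

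Apply the test to the modified ITT population after imputing missing values as SAP 3.2 states, and report observed cases as a sensitivity analysis. Limiting the fallback to observed cases would drop subjects whom SAP 2.2 includes and set aside SAP 3.2, so it should not be the main version.

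Costs: the wording change is small and no data collection changes. The signed rank test gives up baseline adjustment and the repeated-measures model, and pooling over imputations takes a little more work. It assumes roughly symmetric changes, or baseline and follow-up values that are exchangeable under the null. With exponential changes at n = 30 (an assumed, strongly skewed case) it rejected 13.7% of the time when centred at median zero and 15.7% at mean zero. Zero changes are likely to be common on integer items, so their handling should be named. The replacement sentence does not settle when the fallback is triggered; SAP 3.1 still needs a rule for that.

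An acceptable alternative keeps the model, covariate and imputation: rank baseline and visit values jointly, or use signed ranks of change, with the null stated as zero.
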